6.3. Exploratory Endpoints

6.3.1. COVID-19 Incidence Rate (Maternal Participants)

6.3.1.1. COVID-19 Incidence per 1000 Person-Years of Follow-Up Based on Central Laboratory or Locally Confirmed NAAT

6.3.1.1.1. Main Analyses

- Estimands:
 - COVID-19 incidence based on central laboratory or locally confirmed NAAT from 7 days after the second dose of BNT162b2 per 1000 person-years of follow-up in maternal participants who received BNT162b2 at initial randomization ([Section 2.1](#)).
- Analysis set: Evaluable efficacy population (maternal), all-available efficacy population (maternal) ([Section 4](#)).
- Analysis time point: End of the surveillance period.
- Analysis methodology: Incidence rate (per 1000 person-years of follow-up) and 2-sided 95% CI for confirmed COVID-19 illness (using the first definition in [Appendix 2](#)) from 7 days after the second dose of BNT162b2 for participants who received BNT162b2 at initial randomization.
- Intercurrent events and missing data: Missing data will not be imputed.
- Reporting results: Incidence rates and the associated 2-sided 95% CIs will be provided.

6.3.1.1.2. Supplemental Analyses

The same analyses will be performed for confirmed COVID-19 illness based on CDC-defined symptoms (using the second definition in [Appendix 2](#)).

6.3.2. Asymptomatic SARS-CoV-2 Infection (Maternal Participants)

6.3.2.1. Incidence of Asymptomatic SARS-CoV-2 Infection per 1000 Person-Years of Follow-Up Based on N-Binding Antibody Seroconversion

6.3.2.1.1. Main Analyses

- Estimand:
 - Incidence of asymptomatic SARS-CoV-2 infection based on the N-binding antibody seroconversion through 6 months after delivery per 1000 person-years of follow-up in maternal participants who received BNT162b2 at initial randomization and without evidence of prior SARS-CoV-2 infection ([Section 2.1](#)).
- Analysis set: Evaluable efficacy population (maternal), all-available efficacy population (maternal) ([Section 4](#)).

- Analysis time point: End of the surveillance period.
- Analysis methodology: Incidence rate (per 1000 person-years of follow-up) and 2-sided 95% CI for asymptomatic SARS-CoV-2 infection based on the N-binding antibody seroconversion (see [Appendix 2](#) for the definition) through 6 months after delivery for participants who received BNT162b2 at initial randomization and without evidence of prior SARS-CoV-2 infection.
- Intercurrent events and missing data: Missing data will not be imputed.
- Reporting results: Incidence rate and the associated 2-sided 95% CI will be provided.

6.3.3. Serological Response by COVID-19 and SARS-CoV-2 Infection Status (Maternal Participants)

6.3.3.1. Full-Length S-Binding IgG Levels and SARS-CoV-2 Neutralizing Titers

6.3.3.1.1. Main Analyses

- Estimands:
 - GMCs of full-length S-binding IgG levels ([Section 2.1](#))
 - GMTs of SARS-CoV-2 neutralizing titers ([Section 2.1](#)).
 - GMFR from before vaccination to each subsequent time point after vaccination for full-length S-binding IgG levels and SARS-CoV-2 neutralizing titers ([Section 2.1](#)).
- Analysis set: Evaluable immunogenicity population (maternal), all-available immunogenicity population (maternal) (as applicable) ([Section 4](#)) in each subset of maternal participants with confirmed COVID-19 (using the first definition in [Appendix 2](#)), confirmed severe COVID-19 (using the first definition in [Appendix 2](#)), and SARS-CoV-2 infection without confirmed COVID-19 (using the first definition in [Appendix 2](#)).
- Analysis time points: Baseline, 1 month after Dose 2, at delivery, and 6 months after delivery.
- Analysis methodology: GMs and the associated 2-sided CIs will be derived as described in [Section 5.2.2.1](#). GMFRs will be calculated as described in [Section 5.2.2.2](#).
- Intercurrent events and missing data: Concentrations/titers below the LLOQ or denoted as BLQ will be set to $0.5 \times \text{LLOQ}$ for analysis. However, this calculation may be adjusted based upon additional data from the assay. Missing data will not be imputed.
- Reporting results: GMCs/GMTs and 2-sided 95% CIs will be provided for each vaccine group before vaccination and at each subsequent time point after vaccination. GMFRs and 2-sided 95% CIs will be provided for each vaccine group from before vaccination to each subsequent time point after vaccination.

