To describe the incidence of asymptomatic SARS-CoV-2 infection through 6 months after delivery in maternal participants 18 years of age or older vaccinated at 24 to 34 weeks' gestation with BNT162b2 at initial randomization and without evidence of prior SARS-CoV-2 infection.	In maternal participants who received BNT162b2 at initial randomization and without evidence of prior SARS-CoV-2 infection: 
 Incidence per 1000 person-years of follow-up 	
 Incidence of asymptomatic SARS-CoV-2 infection per 1000 person-years of follow-up based on N-binding antibody seroconversion
To describe the serological responses among maternal participants to the BNT162b2 vaccine candidate in cases of: 
 Confirmed COVID-19 Confirmed severe COVID-19 SARS-CoV-2 infection without confirmed COVID-19 	In each subset of evaluable maternal participants from each vaccine group with: 
 Confirmed COVID-19 Confirmed severe COVID-19 SARS-CoV-2 infection but no confirmed COVID-19 GMCs/GMTs and GMFRs at baseline, 1 month after Dose 2, at delivery, and 6 months after delivery 	
 Full-length S-binding IgG levels SARS-CoV-2 neutralizing titers
To describe the immune response to prophylactic BNT162b2 between Dose 1 and Dose 2 when administered to maternal participants 18 years of age or older vaccinated at 27 to 34 weeks' gestation in the Phase 2 portion of the study.	In evaluable maternal participants: 
 GMCs/GMTs at baseline and before Dose 2 GMFRs from baseline to before Dose 2 	
 Full-length S-binding IgG levels SARS-CoV-2 neutralizing titers
To describe the immune response in infants born to breastfeeding maternal participants vaccinated with prophylactic BNT162b2 during pregnancy.	In infants born to maternal participants from each vaccine group, based on the breastfeeding status: 
 GMCs and GMFRs, at birth and 6 months after delivery 	
 Full-length S-binding IgG levels

Objectives ^a	Estimands	Endpoints

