4.2. Scientific Rationale for Study Design

There are currently no licensed vaccines to prevent infection with SARS-CoV-2 or COVID-19. Pregnant women are at risk of acquiring SARS-CoV-2 infection, developing COVID-19 and COVID-19-associated complications. Given the global crisis of COVID-19 and fast expansion of the disease globally, the rapid development of an effective vaccine for use in this population is of utmost importance.

This study is being conducted as a standard maternal immunization safety and immunogenicity clinical trial; however, additional surveillance for COVID-19 has been included as part of the study to assess efficacy (based on a minimal number of cases) as well as to monitor the potential risk of disease enhancement and severe disease in pregnant women and their infants with COVID-19. If a participant experiences symptoms, as detailed in [Section 8.13](#), a COVID-19 illness and subsequent convalescent visit will occur. As part of these visits, samples (nasal swab and blood) will be taken for antigen and antibody assessment as well as recording of COVID-19-related clinical and laboratory information (including local diagnosis).

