8.13.2. Potential Maternal COVID-19 Convalescent Visit (28 to 35 Days After Potential COVID-19 Illness Visit)

- Record AEs, as appropriate as described in [Section 8.3](#). Note: Potential COVID-19 illnesses that are consistent with the clinical endpoint definition should not be recorded as AEs. These data will be captured as efficacy assessment data only on the relevant pages of the CRF, as these are expected endpoints.
- Record details of any of the prohibited medications specified in [Section 6.5.1](#) received by the participant if required for her clinical care.
- Collect a blood sample (approximately 20 mL) for immunogenicity testing.
- Collect/update COVID-19–related clinical and laboratory information (detailed in [Section 8.13.1](#)).
- Complete the source documents.
- The investigator or an authorized designee completes the CRFs.
- Record any AEs that occur within the 48 hours after the blood draw as described in [Section 8.3](#).

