- Record details of any of the prohibited medications specified in [Section 6.5.1](#) received by the participant if required for her clinical care.
- Collect a blood sample (up to 5 mL based on weight [[Table 1](#)]) for immunogenicity testing.
- Collect/update COVID-19–related clinical and laboratory information (detailed in [Section 8.13.1](#)).
- Complete the source documents.
- The investigator or an authorized designee completes the CRFs.
- Record any AEs that occur within the 48 hours after the blood draw as described in [Section 8.3](#).

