Appendix 2. IRR and VE Derivation

COVID-19 Case Definition

Maternal Participants

Two definitions of SARS-CoV-2–related cases, and SARS-CoV-2–related severe cases, will be considered (for both, the onset date of the case will be the date that symptoms were first experienced by the maternal participant; if new symptoms are reported within 4 days after resolution of all previous symptoms, they will be considered as part of a single illness):

Confirmed COVID-19, first definition: presence of at least 1 of the following symptoms and SARS-CoV-2 NAAT-positive during, or within 4 days before or after, the symptomatic period, either at the central laboratory or at a local testing facility (using an acceptable test):

- Fever;
- New or increased cough;
- New or increased shortness of breath;
- Chills;
- New or increased muscle pain;
- New loss of taste or smell;
- Sore throat;
- Diarrhea;
- Vomiting.

The second definition, which may be updated as more is learned about COVID-19, will include the following additional symptoms defined by the CDC (listed at <https://www.cdc.gov/coronavirus/2019-ncov/symptoms-testing/symptoms.html>):

- Fatigue;
- Headache;
- Nasal congestion or runny nose;
- Nausea.

Confirmed Severe COVID-19, first definition: confirmed COVID-19 and presence of at least 1 of the following:

- Clinical signs at rest indicative of severe systemic illness (RR \geq 30 breaths/min, HR \geq 125 beats/min, SpO₂ \leq 93% on room air at sea level, or PaO₂/FiO₂ <300 mm Hg);
- Respiratory failure (defined as needing high-flow oxygen, noninvasive ventilation, mechanical ventilation, or ECMO);
- Evidence of shock (SBP <90 mm Hg, DBP <60 mm Hg, or requiring vasopressors);
- Significant acute renal, hepatic, or neurologic dysfunction*;
- Admission to an ICU;
- Death.

The second definition, which may be updated as more is learned about COVID-19, will include the following additional outcomes defined by the CDC (listed at <https://www.cdc.gov/coronavirus/2019-ncov/need-extra-precautions/people-with-medical-conditions.html>):

- Hospitalization;
- Admission to the ICU;
- Intubation or mechanical ventilation;
- Death.

Infant Participants

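### SAP 6.3.3 groups cases without regard to when infection occurred, so titres at 1 month after Dose 2 and at delivery mix pre- and post-infection samples; no antibody-level analysis names the convalescent sample

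*SAP*

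**What the plan says.** The exploratory objective in Protocol 3 is "To describe the serological responses among maternal participants to the BNT162b2 vaccine candidate in cases of" confirmed COVID-19, confirmed severe COVID-19, and SARS-CoV-2 infection without confirmed COVID-19. Its estimand asks for "GMCs/GMTs and GMFRs at baseline, 1 month after Dose 2, at delivery, and 6 months after delivery". SAP 6.3.3.1.1 repeats the schedule: "Analysis time points: Baseline, 1 month after Dose 2, at delivery, and 6 months after delivery".

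The SAP's subsets rest on case status alone. Results are given "in each subset of maternal participants with confirmed COVID-19 (using the first definition in [Appendix 2"), and likewise for the other two case types. No condition relates the date of infection to the date of the sample, although SAP Appendix 2 defines such a date: "the onset date of the case will be the date that symptoms were first experienced by the maternal participant". For women without clinical COVID-19, the same appendix defines seroconversion as a positive N-binding result after a negative one.

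Protocol 8.13.2 schedules a convalescent visit 28 to 35 days after the illness visit, with the instruction "Collect a blood sample (approximately 20 mL) for immunogenicity testing". Protocol 8.1.3 lists neutralisation, S-binding and N-binding assays for serum from the scheduled visits. The convalescent sample is not a time point in SAP 6.2.2 or 6.3.3, the maternal antibody-level analyses that run past Dose 2.

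**The concern.** The objective is the response to the vaccine among women who became cases. A reader would look for lower titres before breakthrough infection, and separately for how far infection raised titres. A woman infected between the doses contributes a post-infection titre at 1 month after Dose 2. A woman infected three months after delivery contributes pre-infection titres at that visit and at delivery. The plan averages the two. A high value could then be vaccine response or infection boosting, and a low pre-breakthrough titre could be hidden by women already infected when sampled.

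The sample timed to the illness, which would best show the level after infection, has no place in the tables.

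**Working it through.** **Which rows are mixed.** The documents give no case count, share or titre ratio for this analysis, so there is no figure to reproduce. Taking the four time points in turn:

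- *Baseline.* Prior diagnosed COVID-19 is excluded (Protocol 5.2.1, criterion 2) and seroconversion needs an earlier negative N-binding result. Samples therefore essentially precede the infection that defines the subset. The exception is infection found at Visit 1, which Protocol 8.16 allows for.
- *1 month after Dose 2.* Mixed.
- *Delivery.* Mixed.
- *6 months after delivery.* This is the final visit and is scheduled only for women randomised to BNT162b2 (Protocol 1.3.1). Cases are essentially all post-infection by then. Placebo recipients have no such sample.

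**Effect on a mixed row.** Let m be the mean log titre before infection, k the post/pre titre ratio and s the share of case samples taken after infection. The pooled mean is (1 − s)·m + s·(m + log k) = m + s·log k, so the pooled GMT is the pre-infection GMT times k^s. Because baseline is not mixed, the GMFR is multiplied by the same factor.

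**Plausible values of s.** These are illustrative. Taken from the visit windows: Dose 2 on day 21, Visit 4 31.5 days later (day 52.5), and follow-up ending 180 days after delivery (BNT162b2) or 28 days after (placebo, who change schedule at 1 month after delivery). Assumed: first dose at 28 weeks, delivery at 39 weeks (day 77), constant low infection hazard. Follow-up then ends on day 257 or day 105. Counting onset from Dose 2 + 7 days subtracts 28 from every day count.

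The last column is a simulation with first dose spread over 24–34 or 27–34 weeks and delivery over 37–41 weeks. It used the document windows and dropped women who delivered before Visit 4.

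| Row | Onset counted from Dose 1 | From Dose 2 + 7 days | Simulation range |
|---|---|---|---|
| BNT162b2, 1 month after Dose 2 | 52.5/257 = 0.20 | 24.5/229 = 0.11 | 0.10–0.21 |
| BNT162b2, delivery | 77/257 = 0.30 | 49/229 = 0.21 | 0.19–0.31 |
| Placebo, 1 month after Dose 2 | 52.5/105 = 0.50 | 24.5/77 = 0.32 | 0.31–0.54 |
| Placebo, delivery | 77/105 = 0.73 | 49/77 = 0.64 | 0.60–0.74 |

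**Resulting factor k^s over the simulation range.** k is assumed.

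| Row | k = 4 | k = 10 |
|---|---|---|
| BNT162b2, 1 month after Dose 2 | 1.1–1.3 | 1.3–1.6 |
| BNT162b2, delivery | 1.3–1.5 | 1.5–2.0 |
| Placebo, 1 month after Dose 2 | 1.5–2.1 | 2.0–3.5 |
| Placebo, delivery | 2.3–2.8 | 4.0–5.5 |

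With the same k = 10 in both arms and s of 0.20 against 0.50, timing alone would shift an informal between-arm GMT ratio by 10^(0.50 − 0.20) = 2.0.

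The formula treats every post-onset sample as fully boosted, so it overstates the effect for samples taken within days of onset.

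**The case against.** The strongest defence is that the SAP follows the protocol, whose estimand lists the same four time points. A reader might infer that the convalescent sample was drawn for this analysis and then dropped. The documents do not say so. Protocol 4.2 says only that "samples (nasal swab and blood) will be taken for antigen and antibody assessment", alongside a reference to monitoring for disease enhancement. The objective concerns response to the vaccine, for which visits anchored to Dose 2 and delivery are a coherent choice.

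Nor does it follow that the convalescent result goes unused. N-binding is one of the three assays, and the wording of the case definitions in SAP Appendix 2 does not exclude a convalescent N-binding result. What is missing is an antibody-level analysis that names the sample.

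The consequences are also limited. The analysis is exploratory, SAP 5.1 rules out hypothesis tests, SAP 6.3.3 plans no between-arm comparison, and Protocol 4.2 expects a minimal number of cases among about 350 women. Splitting rows will leave some cells nearly empty.

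All of this stands and limits the weight of the point. It does not tell the reader of a pooled row which samples preceded infection.

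**Conclusion.** The point holds for two of the four time points. At 1 month after Dose 2 and at delivery, the GMTs, GMCs and GMFRs combine samples from before and after infection, and the planned output gives no means of separating them. The size is k^s, which rests on values outside the documents; the tables are a guide to scale only. That the mix differs by arm is likely rather than certain, and follows from the different follow-up lengths.

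Two stronger readings should be resisted. One is that every time point is mixed; baseline and 6 months are not, for the reasons given. The other is that the analysis describes neither the vaccine response nor the infection response. Under the stated assumptions, about 79–90% of case samples in the BNT162b2 arm at 1 month after Dose 2 would precede infection, so that row would largely reflect the vaccine. The defect is that the table cannot show this.

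No primary or secondary conclusion is affected. It is a low-cost improvement to an exploratory analysis.

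**What to change.** In SAP 6.3.3:

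1. Flag each sample as before or after symptom onset as defined in Appendix 2. For infection without confirmed COVID-19, use before or after the first positive N-binding (or NAAT) result.
2. At 1 month after Dose 2 and at delivery, report pre- and post-infection values separately. Where cells are small, list individual titres by days since onset.
3. Report convalescent titres for symptomatic cases as a row or listing, showing which earlier sample is available and which doses preceded onset. A single pooled GMFR from the last pre-illness sample would create a new mix. Phase 3 women have no pre-Dose 2 blood draw, so a woman infected between doses has only her baseline value as denominator, while a woman infected after delivery has a post-vaccination one.
4. State that the 6-month row is BNT162b2-only, since the section promises results for each vaccine group at each subsequent time point.
5. Align the estimand text in Protocol 3.

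The cost is SAP and protocol wording, one derived flag and some listings; the blood, assays and onset dates are already planned. The downsides are very small cells, and little or no convalescent sample for infection without confirmed COVID-19, because that visit follows a symptomatic illness visit.

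The infant convalescent sample (Protocol 8.19.2: "Collect a blood sample (up to 5 mL based on weight") is also outside the infant antibody time points of birth and 6 months. A listing of those IgG values is optional and not part of this maternal objective.

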6.3.3.1.2. Supplemental Analyses

The same analyses will be performed in each subset of maternal participants with confirmed COVID-19 (using the second definition in [Appendix 2](#)), confirmed severe COVID-19 (using the second definition in [Appendix 2](#)), and SARS-CoV-2 infection without confirmed COVID-19 (using the second definition in [Appendix 2](#)).

6.3.4. Immune Response After Dose 1 (Phase 2 Maternal Participants)

6.3.4.1. Full-Length S-Binding IgG Levels and SARS-CoV-2 Neutralizing Titers

6.3.4.1.1. Main Analyses

- Estimands:
 - GMCs of full-length S-binding IgG levels ([Section 2.1](#)).
 - GMTs of SARS-CoV-2 neutralizing titers ([Section 2.1](#)).
 - GMFR from before vaccination to each subsequent time point after vaccination for full-length S-binding IgG levels and SARS-CoV-2 neutralizing titers ([Section 2.1](#)).
- Analysis set: Dose 1 evaluable immunogenicity population (maternal), Dose 1 all-available immunogenicity population (maternal) (as applicable) ([Section 4](#)) in maternal participants enrolled in the Phase 2 portion of the study.
- Analysis time points: Baseline and before Dose 2.
- Analysis methodology: GMs and the associated 2-sided CIs will be derived as described in [Section 5.2.2.1](#). GMFRs will be calculated as described in [Section 5.2.2.2](#).
- Intercurrent events and missing data: Concentrations/titers below the LLOQ or denoted as BLQ will be set to $0.5 \times \text{LLOQ}$ for analysis. However, this calculation may be adjusted based upon additional data from the assay. Missing data will not be imputed.
- Reporting results: GMCs/GMTs and 2-sided 95% CIs will be provided for each vaccine group before vaccination and at each subsequent time point after vaccination. GMFRs and 2-sided 95% CIs will be provided for each vaccine group from before vaccination to each subsequent time point after vaccination.

Figures:

Empirical RCDCs will be provided for full-length S-binding IgG levels and SARS-CoV-2 neutralizing titers at baseline and before Dose 2 for each vaccine group ([Section 5.2.2.4](#)).

6.3.5. Immune Response by Breastfeeding Status (Infant Participants)

6.3.5.1. Full-Length S-Binding IgG Levels

6.3.5.1.1. Main Analyses

- Estimands:
 - GMCs of full-length S-binding IgG levels ([Section 2.1](#)).
 - GMFRs from birth to 6 months of age ([Section 2.1](#)).
- Analysis set: Evaluable immunogenicity population (infant), all-available immunogenicity population (infant) (as applicable) ([Section 4](#)) by breastfeeding status.
- Analysis time points: Birth and 6 months of age.
- Analysis methodology: GMCs and the associated 2-sided CIs will be derived as described in [Section 5.2.2.1](#). GMFRs will be calculated as described in [Section 5.2.2.2](#).
- Intercurrent events and missing data: Concentrations/titers below the LLOQ or denoted as BLQ will be set to $0.5 \times \text{LLOQ}$ for analysis. However, this calculation may be adjusted based upon additional data from the assay. Missing data will not be imputed.
- Reporting results: GMCs and 2-sided 95% CIs will be provided for each vaccine group (according to the study intervention the maternal participants randomized) at birth and 6 months of age. GMFRs and 2-sided 95% CIs will be provided for each vaccine group (according to the study intervention the maternal participants randomized) from birth to 6 months of age.

6.3.6. Safety Endpoints by Breastfeeding Status (Infant Participants)

6.3.6.1. Adverse Events

6.3.6.1.1. Main Analyses

- Estimand: The percentage of infant participants reporting AEs from birth through 1 month of age ([Section 2.1](#)).
- Analysis set: Safety population (infant) ([Section 4](#)) by breastfeeding status.
- Analysis time point: Birth through 1 month of age.
- Analysis methodology: Descriptive statistics ([Section 5.2.1](#)).
- Intercurrent events and missing data: Missing data will not be imputed except for partial AE start dates ([Section 5.3](#)).

- Reporting results: Counts, percentages, and the associated Clopper-Pearson 95% CIs for infant participants with AEs from birth through 1 month of age will be provided for each vaccine group (according to the study intervention the maternal participants received).

